### 8.8. Handling of Missing Data

Missing values where the patients have been completely recovered at the last visit will be imputed with the method of last observation carried forward (LOCF).

Other missing values where patients have not been recovered and did not complete follow-up clinic visits will be imputed using worst case last observation carried forward.

The LOCF method will be used for the primary analysis only. For secondary analyses, the complete case analysis will be applied.

In case of incomplete start dates and end dates of adverse events, the "worst case" date will be used. For example, if "December 2020" is recorded as the time of start or end of an adverse event, December 1, 2020 and December 31, 2020, will be used as start- and end-date, respectively.

The last pre-administration observation will be used as the baseline value for calculating post-administration changes from baseline.

For other variables, missing data will result in a reduced sample size for that parameter. A patient who withdraws prior to the last planned observation will be included in the analysis up to the time of discontinuation.

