The study medication including instructions about route of administration and dosage for the specific child will be distributed at the baseline visit. CRFs will be completed by the investigator or study nurse.

One week ±3 days telephone call and two weeks ±3 days telephone call

After one and two weeks, the study nurse will call the child and/or parents/guardians to follow up that study medication is taken according to instructions and to check whether any AEs have occurred. Bottles with remaining study medication will be returned after end of treatment for accountability check. Safety is followed-up by asking for AEs. CRFs will be completed by the study nurse.

One month ± 5 days and 12 months ±2 weeks follow-up visits

After 1 month and 12 months, the child with parents/guardians come to a follow-up at the pediatric or ENT-clinic. Grading of the facial nerve palsy with House-Brackmann and Sunnybrook will be performed. Safety followed-up by asking for adverse events. Also concomitant medications will be updated, if applicable. CRF's will be completed at 1 month and at 12 months by the investigator or study nurse.

The child and the parents/guardians will complete the Facial Clinimetric Evaluation (FaCE) scale, the Facial Disability Index (FDI) at 1 and 12 months follow-up and the Synkinesis Assessment Questionnaire (SAQ) at the 12 months follow-up.

Complementary treatment (for example physical therapy or massage) is asked for at the 12 months follow-up. If the patient has a moderate – severe persistent facial nerve palsy, a visit at an ENT-specialist will be arranged for further evaluation.

End of the study is defined as completed at the 12-months follow-up visit for the last included patient (LSLV). An end-of-the-study CRF for each participant will be completed by the Principal Investigator. The Medical Products Agency and the Regional Ethical Review Board will be informed within 90 days from the date of LSLV.

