12 ASSESSMENT OF SAFETY

Safety will be evaluated by recording of routine laboratory tests (white and red blood cells, CRP, electrolytes and glucose), physical examinations, blood pressure and vital signs measurements. Adverse Events (AEs) or Serious Adverse Events (SAEs), will be reported if occurring during the study period (12 months).

Any clinically relevant changes and actions taken, for instance occurrence of an adverse event or administration of concomitant medication, will be recorded in the CRF and hence in the database.

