12.2 METHODS FOR ELICITING, RECORDING AND FOLLOW-UP OF ADVERSE EVENTS

Information regarding AEs is to be obtained by questioning or examining the subject after having signed the ICF. At each visit all new complaints and symptoms (i.e., those not existing prior to signing of informed consent) must be recorded on the AE CRF.

Pre-existing complaints or symptoms that increase in intensity or frequency after having signed the ICF must also be reported as an AE.

All AEs must be characterized in terms of their start and stop dates, maximum intensity, action taken on the study medication, relationship to study medication, subject outcome and whether or not the AE led to a SAE. Any clinically relevant increase or decrease to the intensity or frequency of a reported AE requires a separate entry on the AE form.

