16.2 RISK - BENEFITS

A risk analysis for this study has been made. These risks together with the actions to minimize these risks are compiled below:

	Anticipated risk	Action
1	Side effects such as minor behavior problems (mood changes), sleep disturbances, nausea or vomiting	Reported as Adverse Events and follow up until recovered. A Development Safety Update Report (DSUR) will be presented yearly to MPA
2	Trauma for the child to take medicine	Capsules may be opened and the content can be mixed with something tasty. The study nurse will instruct the parents/guardians when study medication is distributed and will also follow up how it works by telephone calls one and two weeks after Baseline
3	No effect on the recovery rate	There is no alternative treatment, why there is no risk that the patient looses an effective treatment by participating in the study

A short-course oral treatment with corticosteroids (defined as 1-2 mg/kg once daily in 7-14 days) is not associated with major side effects, such as risk of growth retardation, osteoporosis or diabetes mellitus in children, but may be associated with minor side effects, such as behavioral problems (mood changes), sleeping disturbances, nauseas or vomiting in 4,3 – 5,4 % of cases (17,25,26).

The risk of minor side effects will be reduced with the dose $1 \text{ mg/kg} \times 1$ (17), as we plan on using in the present study.

Increased susceptibility to infection (<1%) is the most frequent (S)AEs associated with short courses of corticosteroids (25,26). In five large RCTs on short-course corticosteroid treatment, three children with varicella infection needed intensive care due to complications (25).

Parents/guardians will be informed before start of treatment in the current study about the importance to attend health care if fever or signs of infection occur during the study period.

In summary, the benefits, i.e. possibly improved recovery of the facial nerve palsy are anticipated being higher than the risks.

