### **8.2. Baseline Characteristics and Treatment Group Comparability**

Demographics and baseline characteristics such as age, sex, weight, blood pressure, NeBoP test etc. will be summarized by treatment group and in total.

Continuous variables such as Sunnybrook-scale will be summarized by number of observations (n), mean, standard deviation (SD), median, minimum (min) and maximum (max). Categorical variables will be summarized in frequency tables (presenting frequencies and proportions). Medical history will be presented in a table and, if appropriate listed as a per-patient data listing. Adverse Events that occur before first treatment will be reported separately as baseline event.

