### 8.7. Safety analyses

Adverse events (AEs) will be presented in per-patient data listings and summarized in frequency tables. A summary table will be presented with number of patients with:

- AEs
- serious AEs
- related AEs
- AE leading to discontinuation

for each treatment and in total.

Adverse events (AEs) will be presented in per-patient data listings and summarized in frequency tables by treatment and in total. AEs will be summarized as number of events and number of patients, respectively, by intensity, seriousness and relationship. SAE will be presented in a separate listing.

Safety profile will be evaluated by comparing number (%) of adverse event (AE) and serious adverse events (SEA) in each group. Difference between groups in safety profile will be compared with Chi2-test or when appropriate, Fischer's exact test.

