## 12. Description of Derived Variables

Duration of AE: stop date minus onset date expressed in days

Variable	Algorithm in words	SAS Variable name
Complete recovery of palsy at month 1 according to SB scale	Healed (1) if sunnybrook scale at month 1 is 100. If sunnybrook at month 1 $\leq$ 99 then patients are considered as not healed (0)	Month1_SB_healed
Complete recovery of palsy at month 12 according to SB scale	Healed (1) if sunnybrook scale at Month 12 visit is 100. If sunnybrook at Month 12 visit $\leq$ 99 then patients are considered as not healed (0)	Month12_SB_ghealed
Complete recovery of palsy at month 1 according to HB scale	Healed (1) if HB scale at Month 1 visit =1. If HB scale at Month 1 visit >1 then patients are considered as not healed (0)	Month1_HB_healed
Complete recovery of palsy at month 12 according to HB scale	Healed (1) if HB scale at Month 12 visit =1. If HB scale at Month 12 visit >1 then patients are considered as not healed (0)	Month12_HB_healed
Compliance (%)	Compliance in % = (total number of capsules (10) minus Number of capsules remaining) * 100/10 (0% - 100%)	Compliance_pct

FaCE scale (Total score will be used)

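### SAP 8.8 dates a month-only AE start to the 1st of the month with no floor at first dose, so an AE in the month of first dose can be dated before treatment (minor)

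*SAP*

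**What the plan says.** SAP 8.8 gives incomplete AE dates a worst-case value. Its only worked example is a month-only date, for which "December 1, 2020 and December 31, 2020, will be used as start- and end-date, respectively". Neither that section, SAP 8.7 nor SAP 12 ties the imputed start to first dose, randomisation or consent.

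Three other statements bear on the result:

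- SAP 8.2: "Adverse Events that occur before first treatment will be reported separately as baseline event".
- SAP 12: "Duration of AE: stop date minus onset date expressed in days".
- Protocol 12.2: "all new complaints and symptoms (i.e., those not existing prior to signing of informed consent) must be recorded on the AE CRF". Pre-existing complaints that worsen after consent are recorded as well.

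On timing, Protocol 8.2 states: "The study medication including instructions about route of administration and dosage for the specific child will be distributed at the baseline visit". Consent is also sought at that visit. The study nurse then telephones at 1 and 2 weeks and asks about AEs.

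**The concern.** The SAP 8.2 split needs an onset date, and SAP 8.8 is the only rule that supplies one when the day is missing. The 1st of the month is a worst case for AE duration, because it makes the event as long as possible. It is not a worst case for deciding whether an event began before or after treatment, because there it moves a possible drug effect to before the drug.

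The imputed date also sits badly with AE recording. Only complaints that are new or worse since consent are recorded, yet for an event in the enrolment month the 1st will usually precede consent. That holds however the SAP 8.2 split is programmed.

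At stake is the content of the baseline-event report and, for the affected events, a duration that includes days before treatment.

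**Working it through.** The documents give no figure on this point, so there is none to reproduce.

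**One case.** First dose on 10 December 2020, true onset on 14 December, start recorded as December 2020. The rule gives 1 December. That is 14 − 1 = 13 days before true onset, and 10 − 1 = 9 of those days precede first dose. With a floor at first dose the start is 10 December: post-dose, and still 14 − 10 = 4 days early, so duration remains conservative.

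**Share of month-only starts misdated.** Let first dose fall on day d of a month of L days, and onset k days later, with k = 0 to K − 1. Assume all (d, k) pairs equally likely. The imputed start precedes first dose when onset is in the same month (d + k ≤ L) and d > 1. For L = 30:

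- K = 10 (the treatment days): d = 2 to 21 gives 20 × 10 = 200 pairs, and d = 22 to 30 gives 9 + 8 + … + 1 = 45. Share = 245/300 = 82%.
- K = 31: 29 + 28 + … + 1 = 435 pairs. Share = 435/930 = 47%.
- K = 365 (the 12-month AE period of Protocol section 12): 435/10,950 = 4.0%.
- k ≥ 30: no pair qualifies, for any month length.

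**Sensitivity to the calendar:**

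| Month length | K = 10 | K = 31 | K = 365 |
|---|---|---|---|
| 28 days | 80.4% | 43.5% | 3.7% |
| 30 days | 81.7% | 46.8% | 4.0% |
| 31 days | 82.3% | 48.4% | 4.1% |
| Real calendar, first doses 2019–2023 | 14,960/18,260 = 81.9% | 26,893/56,606 = 47.5% | 26,893/666,490 = 4.0% |

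**Expected count.** Inputs from the documents are 250 children per arm (SAP 9) and the rate in Protocol 16.2: "sleeping disturbances, nauseas or vomiting in 4,3 – 5,4 % of cases". Assume one event per child, with onset during treatment. The prednisolone arm then has 250 × 0.043 = 10.75 to 250 × 0.054 = 13.5 such events. The share lacking a start day is not in the documents and is assumed. Expected mislabelled events = events × missing-day share × 0.819:

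- 1% missing: 0.09 to 0.11
- 5% missing: 0.44 to 0.55
- 10% missing: 0.88 to 1.11

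The side-effect rate is quoted for courses of 1–2 mg/kg. The same section expects lower risk at the study dose, so these counts lean high for that class of event. The total number of AEs from all causes is not given.

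**The case against.** **The link is inferred.** SAP 8.2 speaks of when events occur, SAP 8.8 does not say that its dates feed that split, and the only documented AE derivation that uses dates is duration, which the rule suits. This stands in part: the mislabelling is conditional. But SAP 8.2 needs a date and no other rule supplies one, and an onset before consent is wrong whichever way the split is programmed.

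**The December case is only an example.** A statistician could apply the worst-case principle differently in the month of first dose. That is possible, but nothing in the text directs it.

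**Few dates will be affected.** This stands. The calls at 1 and 2 weeks cover the treatment period and the days just after, which is where the 82% applies, so month-only starts are least likely there. Both visit schedules first mark AE reporting at the 1-week call, and a start before consent would look inconsistent on review.

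**A stronger reading.** A reader might infer that the rule hides early steroid effects and so biases the between-arm safety comparison. The documents do not support that. SAP 8.7 states: "AEs will be summarized as number of events and number of patients, respectively, by intensity, seriousness and relationship". It gives no onset window and does not say that baseline events are removed from its tables. The AE output shells in Appendix 1 were not available for this review and may settle the point.

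**Conclusion.** The point holds as a minor one. Followed as written, SAP 8.8 normally gives an onset before first dose for a month-only AE in the month of first dose. If that date drives the SAP 8.2 split, a post-dose event is reported as a baseline event.

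The percentages rest on uniform first-dose and onset days and apply only to month-only starts, whose number is unknown. On assumed missing-day rates of 1–10%, the likely result in the prednisolone arm is none or about one event. Larger counts need inputs that the documents do not give: an assumed 20% early-AE rate with 20% month-only starts gives 250 × 0.20 × 0.20 × 0.819 = 8.2.

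The effect shown is confined to safety classification and AE duration. The primary endpoint does not use AE dates, and the related-AE endpoint rests on the investigator's causality rating.

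**What to change.** - **SAP 8.8:** when the partial start month is the month of first dose, impute the later of the 1st and the first-dose date, unless recorded information (for example an end date) shows earlier onset. In other months keep the 1st. If no first-dose date is recorded, use the baseline-visit date, when drug is handed out.
- **SAP 8.2:** classify an AE as a baseline event only when recorded, not imputed, information shows onset before first dose.
- **SAP 8.7 (optional):** say whether baseline events are counted in its tables.

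With the floor in place, no post-dose event is moved to baseline by imputation. The cost is two or three sentences and a small programming change before database lock. The SAP 8.2 split already requires a first-dose date. The downside is that a rare true pre-dose AE may count as post-dose. Such events should be few, because recording starts at consent and drug is supplied at the same visit. Durations for the affected events become somewhat shorter.

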### 8.9. Subgroup analysis

Recovery (at 12 months) between treatment groups will be analysed in the subgroup:  
-children with idiopathic facial nerve palsy or *Borrelia* associated facial nerve palsy

To predict recovery at 12 months follow-up logistic regression analysis will be used by following subgroups:

- diagnosis (*Borrelia* associated/Not *Borrelia* associated)
- treatment (Prenisolone/Placebo)
- age group (1-5, 6-10, 11-14, 15-18)
- gender (Girls/Boys)

Presentation of the results is described in section 8.6.1

Subgroup analysis for comparison between Placebo and Prednisolone at 1 and 12 month for QoL variables and HB/SB scales will be performed (see Appendix 1 table 7)

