## 6. Study design

The FACE study is a randomized double-blind, placebo-controlled, multicenter trial. The study is a randomized two armed intervention study with several well-defined clinical outcome measures with a superiority hypothesis testing in favor for the intervention (prednisolone).

Children with acute facial nerve palsy (idiopathic or *Borrelia*-associated) will be recruited at 17 study centers during 2019-2023 and followed during 12 months. Inclusion and exclusion criteria are set.

The Principal Investigator (a pediatrician) or a co-Investigator (an Ear-Nose-Throat specialist) will be responsible for performing the objective evaluation of the facial nerve function on admission (or one day after) and at the follow-up visits 1 month and 12-months.

Study nurses will take care of parts of the study work, such as performing the one and two weeks telephone calls, collecting questionnaires from the child/parents/guardians, collecting and entering data in the CRFs and being the main contact person for the monitor.

Participants are randomly assigned to prednisolone or placebo. Content in bottles with study drug are blinded and coded after a randomization list in variable blocks without stratification. Bottles with study drug has been distributed to each study center.

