## **8. Description of statistical analysis**

All variables will be presented in summary tables and/or per-patients data listings (when appropriate) within treatment group and in total. Graphical presentations may be used if necessary. Descriptive statistics are defined as frequency (%) tables for qualitative variables and as number of observations, means, standard deviations, medians, Q1, Q3, and minimum and maximum values for quantitative variables. Normality of data will be determined by visual inspection of histograms. No adjustment for covariates will be made.

All statistical tests and confidence intervals will be two-sided. The level of significance will be 5%.

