### 8.5. Primary efficacy analyses

Efficacy of cortisone treatment versus placebo will be compared between intervention group and control group at 12-months follow-up, with the outcome measured with House-Brackmann. Recovery will be defined as HB=1. Comparisons between dichotomous variables (i.e. recovered/not recovered) will be performed between groups using Chi2 (or Fisher's exact test) with risk estimate and 95% confidence interval. Mann-Whitney U-test will be used when comparing score medians for the House-Brackmann grading scale.

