## 8.6. Secondary efficacy analyses

Efficacy of cortisone treatment versus placebo will be compared between intervention group and control group at 12-months follow-up, secondarily with the outcome measured with Sunnybrook scale. Recovery will be defined as SB=100. Comparisons between dichotomous variables (i.e. recovered/not recovered) will be performed between groups using Chi2 (or Fisher's exact test) with risk estimate and 95% confidence interval. Mann-Whitney U-test will be used when comparing score medians for the Sunnybrook grading scale or other continuous variables.

Results for continuous variables will be given as median values with interquartile range (IQR; 25th to 75th percentiles) and dichotomous data (i.e. full recovery/not full recover) as proportions with 95% confidence interval using the normal approximation approach.

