### 8.6.1. Prediction models

Logistic regression analysis will be used to evaluate if recovery at 1 month follow-up can predict recovery at 12 months follow-up. Recovery will be defined as HB=1 and SB=100 at 12 months.

Multivariate models will also be performed with 1 month HB/SB scale and baseline variables. We will test if any baseline variables are independently significant together with the scale (HB/SB) at 1-month, and if they increase the predictive ability in the model.

Results will be presented as p-values, odds ratio and 95% CI. To evaluate the predictive ability, ROC curves will be constructed and number of correct classified observations will be presented together with AUC and sensitivity and specificity at the optimal cut-point.

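### SAP 8.9 compares the arms within idiopathic and within Borrelia-associated palsy, but the supplied text plans no direct estimate of whether the effect differs between them (optional improvement)

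*SAP*

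**What the plan says.** SAP 8.9 opens with "Recovery (at 12 months) between treatment groups will be analysed in the subgroup" and then names "children with idiopathic facial nerve palsy or" Borrelia-associated palsy. The singular wording is loose. SAP 6 describes the recruited children in the same two terms ("Children with acute facial nerve palsy (idiopathic or" Borrelia-associated), so pooling them would come close to repeating the whole-trial comparison. The next list in 8.9 also splits by diagnosis. Two within-cause comparisons is therefore the natural reading.

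The methods for each comparison presumably carry over from the main efficacy sections: chi-square or Fisher's test "with risk estimate and 95% confidence interval" (SAP 8.5), and recovery reported "as proportions with 95% confidence interval using the normal approximation approach" (SAP 8.6). SAP 8 sets two-sided testing at 5%.

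SAP 8.9 also plans a logistic regression for 12-month recovery. It lists diagnosis, treatment, age group and gender as separate items and adds "Presentation of the results is described in section 8.6.1". That section states "Results will be presented as p-values, odds ratio and 95% CI", with ROC curves and AUC. No product of treatment and diagnosis is named there, in SAP 8.5, 8.6, 8.6.1, 8.6.2 or 8.10, or in Protocol 13.2. The output shells (Appendix 1) are cited in SAP 2, 8.9 and 13 but were not supplied.

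**The concern.** Naming cause as the subgroup for a treatment comparison invites the question of whether prednisolone works differently in the two causes. They are managed differently, since Borrelia-associated palsy also receives antibiotics (Protocol 10.6), and Protocol 5.1 intends a positive result to feed into guidelines. Readers will set the two results side by side.

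Two separate tests do not answer that question. The subgroups are smaller than the trial and probably unequal in size, so the same true effect will often reach significance in one and miss it in the other. The likely misreading is that the treatment works in one cause and not in the other. At stake is the interpretation of one secondary analysis.

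**Working it through.** **Inputs from the documents.** Recovery 80% on placebo and 90% on prednisolone, two-sided 5%, 80% power, 430 needed, 10% not followed up, 500 included with 250 per arm (SAP 9). Complete-case analysis for secondary analyses (SAP 8.8). Among children with facial palsy, 65% Borrelia-associated and 35% idiopathic (Protocol 5, a background figure).

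**The plan's own figure.** Exact enumeration of Fisher's test at 215 per arm (430 in total) gives 80.3% power for 80% v 90%, so 430 reproduces. Then 430/(1 − 0.10) = 478, which 500 covers.

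**Assumptions for this point, not plan figures by cause.** The effect is 80% v 90% in both causes, the 65/35 split applies to the trial, and 500 × 0.90 = 450 children are evaluable. Per arm that is 450 × 0.65/2 ≈ 146 Borrelia and 450 × 0.35/2 ≈ 79 idiopathic.

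**Chance that exactly one cause is significant.** Chi-square power by exact binomial enumeration is π_B = 0.680 and π_I = 0.433. The two subgroups are independent, so

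P(exactly one) = π_B(1 − π_I) + π_I(1 − π_B) = 0.680 × 0.567 + 0.433 × 0.320 = 0.386 + 0.138 = 0.524.

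Both are significant in 0.294 of trials and neither in 0.181. With Fisher's test the powers are 0.617 and 0.343, and exactly one is 0.537.

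| Change to the base case | Exactly one significant (chi-square) |
|---|---|
| None | 52% |
| 80% v 85% | 28% (Fisher 23%) |
| 80% v 92% | 43% |
| 80% v 95% | 16% |
| 50:50 split (112 and 112 per arm) | 49% |
| 70/30 split (158 and 68 per arm) | 55% |
| All 500 evaluable | 52% |

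**What a direct contrast would do.** In 400,000 simulated base-case trials, a Wald test of the difference between the two risk differences rejects in 5% of all trials. It rejects in 9% of those where exactly one cause is significant.

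**Precision of the contrast (risk-difference scale).** The variance term per cause is V = 0.8 × 0.2 + 0.9 × 0.1 = 0.25. SE = √(0.25/146 + 0.25/79) = 0.0698. The 95% CI half-width is 1.96 × 0.0698 = 0.137, about 14 points. The difference in effect needed for 80% power is 2.80 × 0.0698 = 0.196, about 20 points. If the 10-point effect exists in one cause only, the test rejects in about 27% of trials (Borrelia only) or 28% (idiopathic only).

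**Choice of scale.** Placebo recovery is taken as 70% in one cause and 85% in the other, in both orders. The log-odds test is a Wald test with 0.5 added to each cell.

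| True situation | Risk-difference interaction rejects | Log-odds interaction rejects |
|---|---|---|
| 10-point gain in both causes (70→80%, OR 1.71; 85→95%, OR 3.35) | 5% | 11–19% |
| Odds ratio 2.25 in both causes (70→84%, 85→92.7%) | 14–16% | about 4% |

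The 2.25 is the odds ratio implied by 80% v 90%: (0.9/0.1)/(0.8/0.2). When placebo rates differ, equality on one scale is inequality on the other, so neither scale is neutral.

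**The case against.** The strongest objection is that nobody plans the inference at risk. No objective or endpoint asks whether the effect differs by cause, and Protocol 13.2 already describes testing in general as possibly hypothesis generating. A reader might infer that the SAP means to compare subgroup p-values; it does not say so. The 52% is the chance of a discordant pair that could be misread, and is not the error rate of a planned analysis. This stands, and it keeps the point optional. The general wording in Protocol 13.2 does not, however, label 8.9 exploratory or say how a difference between causes would be judged.

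Second, Appendix 1 may already contain the contrast, and the phrase about logistic regression by subgroups could cover a model that includes it. A reader might infer that the trial has no interaction analysis at all. The documents support only the narrower statement that the supplied text names none.

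Third, the yield is low, and a reader can derive the contrast from the two independent estimates and their intervals. The low power is real. It argues for showing the wide interval openly, since two p-values hide it.

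Fourth, it is tempting to require the risk difference as the deciding scale. The documents do not support that: SAP 8.5 says only that a risk estimate is given, SAP 8.6.1 reports odds ratios, and the second table under the working shows a cost in either direction.

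Finally, the 65/35 split is not a design input. The result is similar at 50:50 and at 70/30. It depends more on the effect size, and falls to 16% at 80% v 95%.

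**Conclusion.** The point holds as an optional improvement to one secondary analysis. On its natural reading, SAP 8.9 gives each cause its own comparison, and the supplied text plans no direct estimate of whether the two effects differ. With identical true effects of 80% v 90%, a 65/35 split and 450 evaluable children, the two results would disagree on significance in about half of trials. The figure is 28% at 80% v 85% and 16% at 80% v 95%.

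This is not an error in the plan. The primary analysis and the sample size of 500 are unaffected. Confidence is moderate, because Appendix 1 was not available and the mix of causes in the trial is assumed.

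**What to change.** In SAP 8.9, before unblinding:

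1. State that the two causes are analysed separately, using one classification. The section now uses idiopathic in one list and not Borrelia-associated in the next, and SAP 12 derives no diagnosis variable.
2. Report the treatment effect with 95% CI in each cause.
3. Add the treatment-by-cause contrast with 95% CI on one effect scale, chosen and justified in advance.
4. Label the analysis exploratory, and state that any difference in effect is judged from that contrast and not from separate subgroup p-values.
5. State that a non-significant contrast does not show that the effect is consistent across causes.

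If Appendix 1 already holds such a contrast, a sentence in 8.9 pointing to it and naming its scale would cover item 3.

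The cost is a few sentences and one derived estimate, with no new data. The drawback is the low power shown above, so the contrast has to be read through its interval.

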## 9. Determination of sample size

Sample size for the FACE study is calculated on the primary outcome (i.e. number (%)) of patients with total recover of the facial nerve palsy in each intervention group, measured by House-Brackmann grade 1, at 12 months follow-up). An 10% difference of the total recovery rate between groups (80% in placebo group versus 90% in prednisolone group) is an estimation from earlier non-RCT studies, interviews with children/parents (unpublished data) and a test of two independent proportions for estimation of the minimal relevant clinical improvement (MRC). To show that such a difference is significant ( $p < 0.05$ , two-sided test) with 80 % power, a total of 430 patients are needed. However, due to the uncertainty in the assumptions and to that a portion (10%) of patients not taking part of the study follow-up, 500 patients will be included in the FACE study (250 in each group).

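### SAP 8.9 reads as separate prediction models within ten subgroup levels: multivariable fits in the smaller levels risk overfitting, and no test of whether prediction differs is stated

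*SAP*

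**What the plan says.** SAP section 8.9 (Subgroup analysis) states: "To predict recovery at 12 months follow-up logistic regression analysis will be used by following subgroups". The list that follows is diagnosis (two levels), treatment (two), age group (four) and gender (two). For presentation of results it refers to section 8.6.1.

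Section 8.6.1 (Prediction models) first plans a logistic regression of 12-month recovery on 1-month recovery. It then adds: "Multivariate models will also be performed with 1 month HB/SB scale and baseline variables". Baseline variables are to be tested for independent significance alongside the 1-month scale and for any gain in predictive ability. Reported results are p-values, odds ratios, 95% intervals, ROC curves, AUC, correct classifications, and sensitivity and specificity at a cut-point chosen as optimal.

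The baseline variables are not listed or limited in number. Neither document states an interaction test, shrinkage, internal validation or a multiplicity rule for these models. Section 8.8 makes all secondary analyses complete-case. The output shells (SAP Appendix 1) are not part of the text available for this review.

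**The concern.** Whether recovery at 1 month predicts recovery at 12 months is a stated secondary objective, so these models will be read for their clinical message. Two things can go wrong if they are fitted level by level.

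First, non-recovery is the rarer outcome and the smaller levels will hold few of them. A multivariable fit with few events looks better in its own data than it would in new children, and so does a cut-point picked from those data. A cut-point specific to an age group could be taken as a prognostic rule.

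Second, separate fits do not answer whether prediction differs between subgroups. A predictor that is significant in one level and not in another may reflect only a difference in numbers. Some contrast between levels has to be estimated and tested before a difference can be claimed.

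**Working it through.** **Inputs.** SAP section 9: "80% in placebo group versus 90% in prednisolone group"; "with 80 % power, a total of 430 patients are needed"; 500 planned, 250 per arm; "a portion (10%) of patients not taking part of the study follow-up". SAP section 8: two-sided 5% level. SAP section 8.8: complete cases for secondary analyses. Protocol section 5: 65% *Borrelia*-associated, 35% idiopathic. Assumed because the documents do not say: equal age groups, a 50/50 gender split, and the same recovery rate across levels of every factor except treatment.

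**The plan's own figure.** For 80% against 90%, the uncorrected formula gives

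n = [1.960 × √(2 × 0.85 × 0.15) + 0.842 × √(0.8 × 0.2 + 0.9 × 0.1)]² / 0.10² ≈ 199 per arm.

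The continuity correction raises this to 219 per arm, 438 in total, within 2% of the SAP's 430. Fisher's exact test with 215 per arm has 80.3% power. The SAP's 430 is therefore reproduced, and its rates can be used to count events.

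**Levels.** 2 + 2 + 4 + 2 = 10 per scale. Each factor splits the same children, so the levels overlap.

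**Expected House-Brackmann non-recoveries.** Complete cases: 500 × 0.90 = 450. Mean non-recovery: (0.20 + 0.10)/2 = 0.15. Events: 450 × 0.15 = 67.5.

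| Level | Calculation | Events |
|---|---|---|
| Placebo | 225 × 0.20 | 45 |
| *Borrelia*-associated | 67.5 × 0.65 | 44 |
| Each gender | 67.5 / 2 | 34 |
| Idiopathic | 67.5 × 0.35 | 24 |
| Prednisolone | 225 × 0.10 | 22.5 |
| Each age group | 67.5 / 4 | 17 |

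If an age group holds 10% to 40% of the children, its count runs from about 7 to 27. The SAP gives no rate for Sunnybrook = 100, so Sunnybrook events cannot be counted.

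**Events per parameter.** With the 1-month scale plus six baseline variables (assumed), an age group has 17/7 ≈ 2.4.

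**Size of the optimism.** This was simulated. One normal predictor stands for the 1-month scale, all others are noise, and non-recovery is 15%. The cut-point maximises sensitivity plus specificity. Inflation is apparent performance minus performance in a large new sample. Where a range is shown, it covers different strengths of the 1-month scale, and a stronger scale gives less inflation. Single values use a log-odds of 1 per SD.

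| Children (events) | Predictors | AUC inflation | Sensitivity + specificity inflation |
|---|---|---|---|
| 113 (17) | 1 | none | 0.11–0.12 |
| 113 (17) | 4 | 0.06–0.07 | 0.22 |
| 113 (17) | 7 | 0.06–0.11 | 0.22–0.28 |
| 158 (24) | 7 | 0.08 | 0.23 |
| 225 (34) | 7 | 0.06 | 0.17 |
| 450 (67) | 7 | 0.01–0.03 | 0.07–0.10 |

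The four-predictor AUC range reflects two separate runs. One run of the single-predictor case gave 0.13 rather than 0.11–0.12, which is within simulation error.

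**The alternative.** One model with the 1-month scale, treatment, diagnosis, gender and continuous age has 5 parameters, and 6 with one interaction: 67.5/6 ≈ 11 events per parameter.

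**Power for interactions.** As a guide, take a treatment-by-diagnosis interaction with 80% against 90% in one diagnosis group and no effect in the other. The log-odds difference is ln 9 − ln 4 = 0.811. If the effect lies in the *Borrelia* group, the standard error is √[1/(146.25 × 0.16) + 1/(146.25 × 0.09) + 2/(78.75 × 0.16)] ≈ 0.527, and power is Φ(0.811/0.527 − 1.96) ≈ 34%. If it lies in the idiopathic group, power is 31%. A scale-by-factor interaction is a different contrast, but it rests on the same small number of events.

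**The case against.** The strongest reply is that the text does not commit the trial to what is criticised. *By* the listed subgroups could mean that the four factors enter one model as predictors, and protocol section 13.2 describes logistic regression as relating recovery to baseline data. Section 8.9 refers to 8.6.1 only for presentation, so the subgroup models might hold the 1-month scale alone. These readings are possible. The *Subgroup analysis* heading, with treatment arm among the subgroups, favours separate fits. If the factors do enter as predictors, their main effects are tested but still no interaction is stated. One edit to 8.9 settles either reading.

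Three stronger inferences are not supported:

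- *That the models overfit, as a fact.* The number of predictors is not given, and a one-predictor model shows no AUC inflation even at 17 events. The cut-point problem remains for that model.
- *That ten groups share about 70 events, some seven each.* The levels are four overlapping splits, so most hold far more.
- *That subgroup differences are never tested.* This can be said only of the text available, since Appendix 1 is not in it. The SAP also does not say that subgroup p-values or AUCs will be compared.

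It is also fair that these analyses are secondary, that interaction tests will have low power, and that an interaction odds ratio does not directly test a difference in AUC. Hence the exploratory label and the optimism correction in the fix.

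**Conclusion.** The point holds as a cheap improvement. On the natural reading of SAP 8.9, multivariable prediction models in the smaller levels (the age groups, idiopathic palsy, the prednisolone arm) are at high risk of overfitting. At about 17 events and seven predictors the inflation is large enough to mislead. In all 450 children with the same seven predictors it is small for AUC but still visible in sensitivity plus specificity.

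The sizes rest on the SAP's 80% and 90% recovery, 10% loss, equal age groups and genders, equal recovery across levels other than treatment, the 65/35 diagnosis split, and an assumed predictor count. They apply to House-Brackmann only. A reader might infer that every subgroup result would be mostly noise. The counts of 34 to 45 events in the larger levels do not support that.

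**What to change.** In SAP 8.9, replace the separate fits with one logistic model in all children. It should contain the 1-month scale and, as main effects, diagnosis, treatment, gender and age as a continuous variable. Add the scale-by-factor interaction for one factor at a time, and show subgroup odds ratios from that model. Label the interaction tests exploratory because their power is low. Drop subgroup-specific optimal cut-points. For the whole-sample model, report AUC, sensitivity and specificity corrected for optimism by bootstrap, with the choice of cut-point repeated inside each resample.

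The cost is a change of SAP wording, a little bootstrap programming and the loss of subgroup-specific cut-points. Fewer outputs are needed than separate fits would produce.
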